1.0 Research Design

9/17/2024

1.1 Purpose/Specific Aims

The purpose of the study is to conduct an open trial assessing the feasibility and acceptability of a refined heart rate variability biofeedback as a smoking cessation treatment adjunct for individuals who smoke cigarettes.

A. Objectives

The present investigation is an open pilot trial assessing the acceptability and feasibility of a heart rate variability (HRV) biofeedback smoking cessation treatment (HRVB-SCT) for individuals who smoke cigarettes. Primary significant findings will support the integration of HRVB as an acceptable and feasible treatment adjunct to standard smoking cessation treatment. Secondary significant findings will support the expansion of HRVB as a transdiagnostic treatment adjunct that alters cardiac vagal functioning to promote smoking cessation outcomes and emotional and behavioral regulation. Together, primary and secondary findings will support changes to the status quo of cognitive-behavioral intervention approaches and decrease the health and economic burden of smokers who suffer from emotional distress.

The goals are to: (a) assess the acceptability and feasibility of the HRVB intervention as an treatment adjunct to SCT (b) assess changes in smoking behavior and emotional distress and (c) collect additional information to assist in further refining the intervention for a larger R01 RCT.

B. Hypotheses / Research Question(s)

- Primary Analysis: To complete a pilot open trial analyzing the feasibility and acceptability of HRVB-SCT. Intervention feasibility and acceptability will be indexed by measures of i participant attendance and practice adherence, participant self-report ratings of intervention satisfaction, effectiveness, appropriateness, and ease, and therapist reported technological limitations.
- 2. Secondary Analysis: To examine whether smokers receiving HRVB-SCT evidence improvements in: (1) smoking behavior as indexed by self-reported quit-day abstinence, verified by carbon monoxide breath analysis (CO<8ppm); sustained smoking cessation, verified by CO and salivary cotinine levels (<10ng/mg); and self-reported reductions in smoking rate and (2) emotional distress as indexed by self-reported anxiety, mood, and stress ratings. We expect HRVB-SCT will be associated with significant improvements in smoking and emotional health outcomes.

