and group cessation treatments. Following confirmation of pre-screening eligibility criteria participants will be scheduled for their laboratory visit within one week and sent detailed instructions on behaviors to avoid that may confound physiological assessment (e.g., vigorous physical activity or consumption of caffeine within 2 hours, alcohol use within 12 hours). Lab sessions will be scheduled after 12 PM and at least four hours post-usual waking time. This will help control for high urges and withdrawal and low nicotine plasma levels associated with overnight deprivation.

Baseline and Intervention Session 1 (approximately 190 minutes): In order to expedite their baseline appointment, prior to their visit, participants will be emailed the consent form to review ahead of time as well as well as meet with study personnel to review consent and fill out baseline surveys. Afterwards, if found eligible, subjects will be emailed and asked to complete a battery of self-report measures on Qualtrics, an online survey portal. Questionnaire data will be used to assess self-reported symptoms of depression, anxiety and stress, general health, a range of smoking relevant processes, other substance use, and self-reported and behaviorally indexed distress tolerance (see Table 2). If the participant has not completed the self-report battery via Qualtrics prior to the in-person visit, they will complete it via Qualtrics in the lab before proceeding with the rest of the baseline procedures. At the start of the visit, participants will meet with an independent assessor who will verify smoking status via CO analysis of breath sample, re-confirm study inclusion/exclusion criteria and obtain written informed consent. Participants will next complete a physiological assessment during which electrocardiograph and impedance cardiography recordings will be collected. In addition to recording resting levels of participant physiology, participants will also be asked to complete a series of computerized cognitive tasks while physiological recordings are continuously assessed. An objective measure of the participant's height (inches) weight (lbs) will also be collected using the lab's medical grade scale. Because the baseline session also serves as the first respiratory and SCT intervention session, participants will be offered a 1-hour break and snack after completing all baseline assessments and continuing on to complete the remainder of study visit procedures.

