| Week 3 ^v (1W post- quit) | SCT S4 | Review homework Goals: Highlight successes, troubleshoot potential barriers to quitting, preventing relapse Assess NRT use side effects, questions/concerns, adherence | 30 | \$10 |
| | HRVB S4 | Biofeedback practice session Goal: Review and adjust Inner Balance HRVB Make post-quit adjustments to HRVB, assess adherence, motivation Assign homework: Practice 4x/day for at least 20m | 30 | |

9/28/2022 9/17/2024

| | EMA | Assess homework compliance and surveys cravings, withdrawal, distress, and relaxation symptoms | | up to \$105 for HW practice |
|---|---------|--|----|--------------------------------|
| Week 4 ^v (2W post- quit) | SCT S5 | Review homework Assess abstinence status, revise quit plan to maintain abstinence or resume cessation, Provide additional NRT | 30 | \$10 |
| | HRVB S5 | Biofeedback practice session Goal: Assess adherence, motivation, trouble-shoot Assign homework: Practice 4x/day for at least 20m | 30 | |
| | EMA | Assess homework compliance and surveys cravings, withdrawal, distress, and relaxation symptoms | | up to \$105 for HW practice |
| Week 5 ^v | HRVB S6 | Biofeedback practice session Goal: Assess adherence, motivation, trouble-shoot Assign homework: Practice 4x/day for at least 20m | 30 | \$10 |
| | EMA | Assess homework compliance and surveys cravings, withdrawal, distress, and relaxation symptoms | | up to \$105 for HW practice |
| Week 6 ^L (1M post- quit) | IA | 1MFU Survey Recording session: Baseline, Plain Vanilla, Dot Tracking | 50 | \$35 |
| | SCT S6 | Assess quit status via CO analysis Goal: Assess abstinence status, offer of support, encourage resumption, provide additional NRT | 30 | |
| | HRVB S7 | Recording session Goal: obtain commitment to continue practice | 30 | |
| | EMA | Assess homework compliance and surveys cravings, withdrawal, distress, and relaxation symptoms | | up to \$105 for HW practice |

9/28/2022 9/17/2024

| Week 15 ^L (3M post- quit) | IA | • | Assess abstinence via CO and cotinine Recording session: Baseline, Plain Vanilla, Dot Tracking | 60 | \$50 for attending 3 mo F/U \$50 bonus for |
|--|-----------------------------|---|---|----|---|
| | Research Coordinat or | • | 3MFU survey, Exit interview | 30 | attending 6/7 sessions |

^LIn-lab intervention session; ^VVirtual intervention session

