| technological issues, distractions in participant remote environment and their respective influence on treatment delivery. Carbon Monoxide Analysis of Breath Sample: CO analysis will be used to verify eligibility and abstinence status. Analysis will rely on the Bedfont handheld piCO Smokerlyzer and iCOquit Smokerlyzer, which will be used for in-person and remote verification, respectively. Daily Information Sheet: Details participants' cigarette use, alcohol consumption, substance use, medications, meals consumed, and NRT-related side effects Craving/Withdrawal Visual Analog Scale (CW-VAS): Measures X X X X X X X X X X X X X X X X X X X | | | | | | | |
| their respective influence on treatment delivery. Carbon Monoxide Analysis of Breath Sample: CO analysis will be used to verify eligibility and abstinence status. Analysis will rely on the Bedfont handheld piCO Smokerlyzer and iCOquit Smokerlyzer, which will be used for in-person and remote verification, respectively. Daily Information Sheet: Details participants' cigarette use, alcohol consumption, substance use, medications, meals consumed, and NRT-related side effects Craving/Withdrawal Visual Analog Scale (CW-VAS): Measures X X X X X X | | | | | | | |
| Carbon Monoxide Analysis of Breath Sample: CO analysis will be used to verify eligibility and abstinence status. Analysis will rely on the Bedfont handheld piCO Smokerlyzer and iCOquit Smokerlyzer, which will be used for in-person and remote verification, respectively. Daily Information Sheet: Details participants' cigarette use, alcohol consumption, substance use, medications, meals consumed, and NRT-related side effects Craving/Withdrawal Visual Analog Scale (CW-VAS): Measures X X X X X X X X X X X X X X X X X X | | | | | | | |
| used to verify eligibility and abstinence status. Analysis will rely on the Bedfont handheld piCO Smokerlyzer and iCOquit Smokerlyzer, which will be used for in-person and remote verification, respectively. Daily Information Sheet: Details participants' cigarette use, alcohol consumption, substance use, medications, meals consumed, and NRT-related side effects Craving/Withdrawal Visual Analog Scale (CW-VAS): Measures X X X X X | | X | | X | | X | X |

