1.6 Study Variables and Outcomes

To inform a subsequent clinical trial, our analytic plan focuses on the use of descriptive and inferential statistics.

Primary Outcomes:

9/17/2024

Aims 1.a. and 1.b.: Feasibility and Acceptability:

Descriptive statistics will be used to assess feasibility and acceptability of HRVB (see 1.a. Intervention feasibility and 1.b. Intervention acceptability). Ratings of perceived effectiveness, appropriateness, satisfaction, and ease of the intervention are made on a 5-point Liker-type scale ranging from 0-completely disagree to 4-completely agree. Descriptive statistics will also be used to assess participant attendance, adherence, indexed by time spent using the intervention. Instances of technological limitations will be indexed both by count as well as qualitative descriptors (e.g., inner balance device failure to pick up recording; Bluetooth connection errors, etc.).

Secondary Outcomes:

Aim 2.a: Changes in smoking behavior:

Descriptive statistics will be used to report total number and percent of participants reporting abstinence on their quit day using the intent-to-treat sample as well as those who remain in treatment.

Sustained smoking cessation will be assessed descriptively using point prevalence abstinence defined by self-reported abstinence verified by both carbon monoxide analysis of breath sample and saliva cotinine. Paired sample t-tests will be used to assess changes in smoking rate within participants from baseline to quit day, two-week, one-month, and three-month follow-up, as a proxy for harm reduction.

Aim 2.b.: Changes in emotional distress:

Paired sample t-tests will be used to assess changes in emotional distress, including depression, anxiety and stress, within participants, from baseline to two-week, one-month, and three-month follow-up.

We will also examine correlations between baseline emotional distress ratings and key outcomes, including feasibility and acceptability ratings, changes in smoking behavior, and emotional distress to evaluate whether the intervention may be particularly beneficial for smokers with elevated emotional distress.

The following list of measures will be used to assess primary and secondary outcomes of interest:

1.a: Intervention feasibility

| Outcome | Method | Time Frame |
|------------------------|---|-------------------------------------|
| Participant Attendance | Number of attended sessions out of 7 possible | 7 weeks |
| | sessions | |

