| Practice Adherence | Time (in minutes) spent practicing the breathing | 7 weeks |
| | intervention | |
| Intervention | Participant self-report items assessing how effective | Week 1 (i.e., treatment initiation) |
| Effectiveness | the intervention was in helping participants quit and | and Week 16 (i.e., 3-MFU) |
| | manage emotional distress | |
| Intervention | Participant self-report items assessing intervention | Week 1 (i.e., treatment initiation) |
| Appropriateness | comprehension and fit | and Week 16 (i.e., 3-MFU) |
| Intervention Ease | Participant self-report items assessing ease of use | Week 1 (i.e., treatment initiation) |
| | and fit into daily lifestyle | and Week 16 (i.e., 3-MFU) |
| Technological | Interventionist self-report items assessing incidences | 7 weeks |
| Limitations | of technical issues and related effects on intervention | |
| | delivery | |

1.b. Intervention acceptability

9/17/2024

| Outcome | Method | Time Frame |
|-------------------------|---|---|
| Satisfaction and Liking | Self-report items assessing satisfaction with learning the intervention, liking the intervention, breathing techniques, nicotine replacement, and recommending the intervention to others | Week 1 (i.e., treatment initiation) and Week 16 (i.e., 3-MFU) |

2. Secondary Outcome Measures:

2.a. Changes in smoking behavior

| Outcome | Method | Time Frame |
|--------------------------------|---|---|
| Quit-day abstinence | Self-reported abstinence on Quit Day, verified with carbon monoxide analysis of breath sample (CO < 8ppm) | Week 3 (i.e., Quit Date) |
| Sustained Smoking Cessation | Self-reported abstinence, verified carbon monoxide analysis, and salivary cotinine (<10 ng/mL) at study termination | Week 16 (i.e., 3-MFU) |
| Smoking rate | Timeline Followback interview assessing changes in smoking rate | Week 0 (i.e., Baseline,) Week 3 (i.e., Quit Date), 5 (i.e., 2-WFU), Week 7 (i.e.,1-MFU) and Week 16 (i.e., 3-MFU) |

2.b: Changes in emotional distress (i.e., anxiety, depression, and stress)

| Outcome | Method | Time Frame |
|--------------------|--|--|
| Emotional Distress | Self-report items assessing past 2-week ratings of depression, anxiety, and stress | Week 0 (i.e., Baseline,) Week 5 (i.e., 2-WFU), Week 7 (i.e.,1-MFU) and Week 16 (i.e., 3-MFU) |

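### The change in smoking rate rests on self-report alone and is read as harm reduction, while in-lab breath CO is used only as a pass/fail check and the 1-month reading enters no outcome

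*Combined protocol and SAP*

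**What the plan says.** Section 1.1 B names "self-reported reductions in smoking rate" as one index of smoking behaviour. The outcome table in 1.6 (2.a) gives its method as "Timeline Followback interview assessing changes in smoking rate". Sections 1.6 (Aim 2.a) and 6.5 plan paired t-tests for "changes in smoking rate within participants from baseline to quit day, two-week, one-month, and three-month follow-up, as a proxy for harm reduction". The other two smoking outcomes, quit-day abstinence and sustained cessation, are biochemically verified and only described. Smoking rate is therefore the only smoking outcome that is significance-tested, and cigarettes per day is one of the outcomes named in the sample-size paragraph (1.5).

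Breath CO is measured in the lab three times:
- **Baseline (1.3):** the independent assessor will "verify smoking status via CO analysis of breath sample".
- **Week 6, 1 month (Table 1, SCT S6):** "Assess quit status via CO analysis".
- **Week 15, 3 months (Table 1):** together with cotinine.

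Table 2 states the purpose: "CO analysis will be used to verify eligibility and abstinence status". It also marks a CO reading at quit day, which falls in a virtual week. It assigns one device type to in-person readings and another to remote ones.

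**The concern.** In a paired change without a control arm, nothing cancels a systematic difference between how participants report at baseline and how they report later. Participants know what they receive and are counselled to quit, so some drift towards lower reported counts after baseline is plausible. The plan guards against this for abstinence but not for smoking rate.

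Harm reduction is also a statement about exposure, and a count of cigarettes is not a measure of exposure. The trial will hold an exposure measure at the two visits that matter most, yet no analysis uses its value in ppm. Two things are at stake. A self-reported fall could be presented as harm reduction with no biochemical check. And the end-of-treatment visit yields no verified smoking result although the reading is taken. Section 1.5 makes a larger trial conditional on observed effect sizes, so the result may carry weight beyond this pilot.

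**Working it through.** **1. Where each CO reading goes.**

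| Reading | Use in the plan | Used in ppm? |
|---|---|---|
| Baseline, in lab | Eligibility, at least 8 ppm (4.1) | No |
| Quit day, remote | Abstinence, below 8 ppm (1.6, 2.a) | No |
| 1 month, in lab | Quit status within SCT S6; no outcome | No |
| 3 months, in lab | Abstinence, with cotinine (1.6, 2.a) | No |

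The 1-month reading cannot enter sustained cessation. That outcome requires cotinine, which Table 2 schedules only at 3 months, and the outcome table ties it to the 3-month visit.

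**2. The plan's own figure.** Section 1.5 says N=30 suffices for 80% power at alpha 0.25 and d=0.40. Sidedness is not stated. Two-sided, with noncentrality 0.40 × √30 = 2.19 and critical t (29 df) 1.174, power is 84.5%. The required n is 26, or by normal approximation ((1.150 + 0.842)/0.40)² = 24.8, so 25. The detectable d at 80% power is 0.367. One-sided, n=15 is enough. So N=30 is sufficient as stated, and the point does not depend on that statement.

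**3. Smallest significant fall.** Two-sided, 30 pairs: 1.174/√30 = 0.214 SD of the change. If that SD is 5 to 10 cigarettes/day (an assumption; the documents give none), this is 1.1 to 2.1 cigarettes/day.

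**4. Effect of a reporting shift with no true change.** Noncentrality is shift × √30. The shifts are illustrative.

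| Shift (SD of change) | P(significant reduction) | P(significant, either direction) |
|---|---|---|
| 0 | 12.5% | 25% |
| 0.1 | 27% | 32% |
| 0.2 | 47% | 49% |
| 0.3 | 68% | 69% |
| 0.4 | 84% | 85% |

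In cigarettes/day, on the same assumed SD: d=0.20 needs a shift of 0.20 × 5 = 1 to 0.20 × 10 = 2, and d=0.40 needs 0.40 × 5 = 2 to 0.40 × 10 = 4.

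**5. What CO could detect.** At 80% power and two-sided alpha 0.25, the detectable standardised CO change is 0.37 with 30 pairs, 0.41 with 24 and 0.48 with 18 (24 and 18 are assumed retention). No SD of CO is given, so this cannot be put in ppm.

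**6. Limit of CO as a check.** The baseline reading is also the entry gate. If screened CO is roughly normal with mean m, SD s and repeat correlation r, and true smoking is unchanged, the expected fall is (1 − r) × s × λ, where λ = φ(a)/(1 − Φ(a)) and a = (8 − m)/s. The variance of the change is (1 − r)² × s² × (1 + aλ − λ²) + s² × (1 − r²). All inputs are assumed:
- m=20, s=10, r=0.8: a=−1.2, λ=0.219, fall 0.2 × 10 × 0.219 = 0.4 ppm; SD of change 6.2, d=0.07.
- m=12, s=6, r=0.5: a=−0.667, λ=0.427, fall 0.5 × 6 × 0.427 = 1.3 ppm; SD of change 5.6, d=0.23.
- m=12, s=10, r=0.5: a=−0.4, λ=0.562, fall 0.5 × 10 × 0.562 = 2.8 ppm; SD of change 9.3, d=0.30.

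Some CO fall is therefore expected from selection alone. The absence of a fall would be the more informative result.

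**The case against.** The strongest reply is that this is a secondary outcome in an uncontrolled feasibility pilot. The plan openly calls the measure self-reported and the interpretation a proxy, and even a perfectly measured reduction could not be attributed to HRVB when everyone also receives patches and counselling. All of that stands. It limits the weight of the point but does not remove it, since the check costs almost nothing.

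Several stronger readings are tempting, and the documents do not support them:
- **That payment drives under-reporting.** Pay is for attendance and verified breathing practice. Section 4.4 says full compensation does not depend on the ability to make a quit attempt.
- **That participants are under weekly counselling throughout.** SCT has six sessions, none in Week 5 and the last at Week 6, so this does not describe the 3-month report. CO is also due at three of the four tested follow-ups, which may discourage under-reporting.
- **That CO is taken at a standardised time of day.** "Lab sessions will be scheduled after 12 PM and at least four hours post-usual waking time" sets only a lower bound. Time since the last cigarette is not fixed. Baseline CO comes at the start of the visit, while Week 6 CO is listed after a 50-minute recording row. If the table order is the visit order, extra smoke-free time would favour a fall.
- **That a bias of known size exists.** A shift of 2 to 4 cigarettes/day would be large for someone smoking 5 to 9 a day (2/9 = 22% to 4/5 = 80% of intake), and no true reduction at all is an extreme case.
- **That the larger-trial decision hangs on smoking rate.** The paragraph in 1.5 covers emotional distress as well.

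**Conclusion.** The point holds as a low-cost improvement that should be made. The only significance-tested smoking outcome is uncorroborated self-report interpreted as harm reduction, while in-lab CO at baseline, 1 month and 3 months is never analysed as a value and the 1-month reading is in no outcome. At the plan's alpha, a shift of a few tenths of an SD in reporting is enough to make a significant reduction likely. That statement assumes a two-sided test, 30 complete pairs and no true change. The shifts and the SD of 5 to 10 are illustrative and do not show that such bias will occur.

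A reader might infer that a parallel CO fall would establish harm reduction. It would not. The entry threshold produces some regression to the mean, and CO reflects recent smoking at an uncontrolled interval since the last cigarette.

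**What to change.** In 1.6 (2.a) and 6.5:

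1. Report change in in-lab breath CO (ppm) from baseline to 1 month and to 3 months, with confidence intervals, beside the change in cigarettes/day. State that it is corroboration and does not replace the count.
2. Add self-reported abstinence verified by CO below 8 ppm at 1 month, over all enrolled participants, with missing CO not counted as verified.
3. Label the rate outcome as self-reported cigarettes/day. Make no harm-reduction statement if CO does not fall, and describe a CO fall as supportive, not conclusive, giving the two reasons above.
4. Describe the quit-day and two-week changes as self-report only, since no in-lab CO corroborates them.

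The least change that would still help is to drop the harm-reduction wording and label the outcome as self-reported.

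Cost: analysis-plan wording and a few table rows. No new measurement and no extra participants are needed. The downside is one more noisy secondary measure to interpret.

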1.2 Research Significance

Cigarette smokers are disproportionately affected by mood and anxiety disorders (Lawrence, Mitrou & Zubrick, 2009), which impede cessation (Piper, Cook, Schlam, Jorenby & Baker, 2011; Zawertailo & Selby, 2015; Williams, Steinberg, Griffiths & Cooperman, 2013). This Stage II study will further test the feasibility, acceptability, and efficacy of an integrated, biobehavioral, transdiagnostic smoking intervention for individuals who smoke cigarettes. The neurovisceral integration model (Thayer & Lane, 2000; Park & Thayer, 2014) suggests that cardiac vagal functioning plays a critical role in the effective modulation of physiological, emotional, and cognitive processes necessary for self-regulation. Dysregulation in this system is observed across various forms of psychopathology (Moon, Lee, Kim & Hwang, 2013) and cigarette smoking (Thayer & Lane, 2000; Park & Thayer, 2014; Thayer, Ahs, Fredrikson, Sollers & Wager, 2012; Park, Van Bavel, Vasey & Thayer, 2013). Moreover, cardiac vagal activity is associated with emotional disorder severity and recovery (Jain, Cook, Leuchter, et al. 2014; Rottenberg, Salomon, Gross & Gotlib, 2005) as well as smoking onset and maintenance (Ashare, Sinha, Lampert, et al, 2012; Libby, Worhunsky, Pilver & Brewer, 2012; Crane, Gorka, Giedgowd, et al., 2016). HRVB interventions offer a simple and effective means of promoting self-regulation via restoration of the vagal system (Lehrer, Vaschillo E, Vaschillo B, et al., 2003; Lehrer, Vaschillo E, Vaschillo B., 2000; Lehrer & Vaschillo, E, 2004) but have not been applied to smokers with moderate emotional distress. Via the application of HRVB, the current proposal will target the vagal system to improve adaptive and flexible self-regulation (Kashdan & Rottenberg, 2010), thereby supporting smoking cessation and emotional health. Thus, a primary aim of this proposal is to develop and pilot test HRVB as a feasible, acceptable, and effective treatment adjunct for standard smoking cessation treatment (HRVB-SCT) in daily smokers.

9/17/2024

Based on a strong body of empirical work demonstrating the benefits of HRVB in reducing anxiety (Henriques, Keffer, Abrahamson, & Horst 2011) and depressive symptoms (Patron et al., 2013; Rene, 2008) a secondary aim of this proposal is to evaluate the efficacy of HRVB-SCT in improving smoking and emotional health outcomes among adults who smoke. Transdiagnostic processes that promote avoidance and escape of emotional distress are implicated in the development and maintenance of cigarette smoking dependence (Baker, Piper, [name], Majeskie & Fiore, 2004), and may also explain why individuals with depressive and anxiety symptoms are more susceptible to cigarette smoking dependence and poor cessation outcomes (Leventhal & Zvolensky, 2015). Existing smoking cessation interventions informed by these models largely rely upon cognitive-behavioral strategies (Gifford, Kohlenberg, Hayes, et al., 2011; Brown, Reed, Bloom, et al., 2013.) However, automatic visceral responses to emotional distress may impede the utilization of intentional self-control strategies. Biobehavioral interventions that directly address transdiagnostic physiological processes may offer a more targeted means of improving outcomes, thereby identifying an alternative treatment mechanism. Moreover, the development of biobehavioral interventions may improve smoking cessation outcomes for smokers with moderate emotional distress who are not responsive to, or are less receptive of, cognitivebehavioral interventions.

The proposal will use a staged model for developing and standardizing behavioral interventions, as indicated by NIDA. The first phase (i.e., Phase 1A) of the project has focused on drafting, piloting, and modifying an integrated HRVB smoking cessation treatment (HRVB-SCT). The second phase of the project (Phase 1B) will focus on assessing the acceptability and feasibility of treatment delivery, fidelity, and potential for improving smoking cessation outcomes and reducing emotional distress. Data collected during this time will also potentially inform a larger R01 application of a RCT of HRVB-SCT to evaluate smoking and emotional distress outcomes and explore transdiagnostic physiological and cognitive-affective treatment mechanisms.

